4.2 Release to Investigators

No investigational device will be released until the Investigator has received Ethic Committee and Regulatory Approval to conduct the study. Once released to the Investigator, all investigational device inventories will be monitored and accounted for throughout the course of the study.

All investigational devices will be stored in a secure location, segregated from any commercial inventory to minimize the possibility of a study device being used in a non-study patient. Study devices will be labeled "Exclusively for Clinical Investigation".

All unused investigational devices will be returned to Neptune Medical Inc at the end of the study.

- After removal of the Vertex Pulmonary Embolectomy System and the guidewire, continue to manage subject as medically appropriate.
- Complete the procedure per standard institutional guidelines for pulmonary artery thrombectomy procedures and transfer the subject to ICU (if appropriate) or post-surgical ward to monitor subject safety according to institutional guidelines.
- Continue to monitor for vital signs, oxygenation, and new symptoms.
- For symptomatic residual clot, distal embolization, or new PE, continue to treat with anticoagulation.
- Record adverse events/device deficiencies and technical complications as applicable.
- Post-procedure, the Investigator will review all images, clinically assessing the PE status and looking for evidence of vessel injury (perforation/dissection).
- Devices should be disposed of in accordance with applicable local regulations and site procedures following use.

The thrombectomy procedure using the Vertex Pulmonary Embolectomy System shall be aborted if the following occur in the opinion of the Investigator:

- Hemodynamic collapse
- Signs of vascular rupture

5.1 Procedural Screen Failure

5.1.1 Access Failures

There may be cases where the Vertex Pulmonary Embolectomy System is not used due to access failure. Access failure is defined as:

- 1) the guidewire cannot be introduced,

2) or vessel spasm precludes continuing the procedure.

If an adverse event occurs prior to discharge, subject will be followed for safety through discharge. A study exit form (CRF) is required for these Subjects.

5.1.2 Operative Screen Failures

The following subjects are considered operative failures:

- Any eligible patient in whom the Vertex Catheter is not able to be introduced into the pulmonary artery for any reason.
- Until any point prior to the introduction of the Vertex Pulmonary Embolectomy System, the procedure may be converted to another therapeutic treatment or discontinued without the patient receiving any investigational treatment.

No further information will be collected on this patient; a study exit form (CRF) is required for all these patients. Any patient that experiences an adverse event after venous puncture but in whom the Vertex Catheter is not inserted will be monitored through discharge for safety and information about AEs will be collected in CRF, if applicable.

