**ABBREVIATIONS**

Abbreviation	Abbreviated Term	Definition
CDA	Confidential Disclosure Agreement	A contract through which the parties agree not to disclose information covered by the agreement.
CDT	Catheter-Directed Thrombolysis	Percutaneous procedure used to dissolve blood clots (thrombus) by administering a lytic directly into the clot through a catheter.
CSA	Clinical Study Agreement	A contract through which the parties agree upon terms and conditions of a basic relationship between investigational site and a sponsor.
CTA	Computed Tomography Angiography	A specialized X-ray that examines blood flow in blood vessels when they are filled with a contrast material.
FDF	Financial Disclosure Form	Term referring to the requirement of an applicant (i.e., Sponsor) for a marketing application to certify the absence of certain financial interest of Clinical Investigators or to disclose those financial interests.
ITT	Intent to Treat	All patients who provide written informed consent, meet the inclusion/exclusion criteria, and in whom the Vertex Catheter is introduced past the pulmonic valve; enrollment occurs when Vertex Catheter is introduced past the pulmonic valve. Any patient enrolled into the trial, but in whom the Vertex Pulmonary Embolectomy System is not able to access a pulmonary embolus is considered an Intent to Treat patient
NPI	National Principal Investigator	Study advisors who provide study leadership and guidance; they oversee all clinical study activities including clinical investigation plan development and any changes that may be desired or required during the conduct of the study.
Vertex PES	Vertex Pulmonary Embolectomy System	All components of the Vertex Pulmonary Embolectomy System which comprise of the Vertex Catheter, Meridian Catheter, and the Meridian Extraction Set.

TERMS AND DEFINITIONS

Category	Term or Phrase	Definition
Alternative Therapy	Catheter-Directed Therapy	Pharmacomechanical delivery of intrapulmonary thrombolytics, with or without ultrasound assistance.
Alternative Therapy	Mechanical Thrombectomy Device	An alternate EMA-cleared catheter-based device designed to remove or dissolve blood clot.
Alternative Therapy	Medical Therapy	Includes the use of anticoagulation therapy alone and/or systemic thrombolytics.
Alternative Therapy	Surgical Embolectomy	Surgical removal of the pulmonary embolism.

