Event Severity	Mild	No limitation of usual activities, no therapy or only symptomatic therapy required to treat the injury or illness.
Event Severity	Moderate	Some limitation of usual activities or specific therapy is required.
Event Severity	Severe	Inability to carry out usual activities, hospitalization, emergency room treatment, life-threatening events, or death.
Injury	Cardiac Injury	Cardiac injury is defined as any damage to the heart requiring intervention to avoid permanent injury. Examples of possible cardiac injury : Acute heart failure • Acute myocardial infarction • Arrhythmia requiring intervention • Cardiac hematoma • Tricuspid or Pulmonic valve damage
Injury	Pulmonary Vascular Injury	
Pulmonary vascular injury is defined as perforation or injury of a major pulmonary arterial branch requiring intervention to avoid permanent injury.
 
Examples of possible pulmonary vascular injury: Arterial Venous Fistula • Dissection • Hemorrhage • Intimal flap • Perforation • Rupture • Thromboembolic occlusion resulting in permanent damage i.e. infarction

Study Population	Operative Screen Failure	Any eligible patient in whom the Vertex Catheter is not attempted or placed for any reason. Up until this point, the procedure may be converted to another therapeutic treatment or discontinued without the patient receiving any investigational treatment.
Study Population	Intent to Treat (ITT)	All patients who provide written informed consent, meet the inclusion/exclusion criteria, and in whom the Vertex Catheter is introduced past the pulmonic valve; enrollment occurs when Vertex catheter is introduced past the pulmonic valve. Any patient enrolled into the trial, but in whom the Vertex Pulmonary Embolectomy System is not able to access a pulmonary embolus is considered an Intent to Treat patient
Study Population	Screen Failure	Any screened patient who signs the ICF but does not meet the inclusion and exclusion criteria.

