2.8 Subject Screening

Patients will be screened to determine their initial eligibility and interest in the study. in the Inclusion/Exclusion criteria. Informed consent will be obtained once a patient has satisfied screening criteria and prior to any study-specific procedures that are not part of the standard of care. All patients screened will be documented on the Screening/Enrollment Log.

Medical Screen failures will be defined as follows

- **Screen Failure:** Any screened patient who signs the ICF but does not meet all the inclusion or meets any of the exclusion criteria and also such who signed ICF but for whom the Vertex catheter was not introduced and past the pulmonic valve. All patients screened will be documented on the Screening/Enrollment Log. The reason for screen failure will be captured on the log and in the screening/enrollment section of the database. For operative screen failures please refer to section 5.1. for further details.

For Procedural screen failure definitions please refer to *section 5.1*

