11.5 Adverse Event Reporting

Subjects will be carefully monitored during the study for possible adverse events. Safety will be assessed by collecting adverse event/device deficiency data on each patient and will be captured in the CRFs. Any adverse event/device deficiency occurring since subject signed ICF will be recorded in the subject's CRF.

Note: Any medical condition that is present at the time that the subject is screened will be considered as baseline and not reported as an adverse event further in the study. However, if that subject's condition deteriorates at any time during the study, it will be recorded as an AE.

Appropriate treatment will be initiated and the study follow-up will continue as completely as possible.

Planned hospitalization for a pre-existing condition, or a procedure required by the CIP, without serious deterioration in health, is not considered a Serious Adverse Event.

Out of range (abnormal) laboratory value(s) should be captured as an AE(s) if clinically significant.

Ongoing AE should be reviewed and updated at each visit, if applicable. AE will continue to be recorded throughout the study including the follow-up until study exit.

The Investigator will document all observations and clinical findings of adverse events, including the nature, date of onset and stop date (if applicable), severity, seriousness, action(s) taken/treatment, outcome and relationship to the investigational medical device/study procedure(s), on the appropriate eCRFs in the EDC. Whenever possible, available source documentation should be provided to the Sponsor.

The Investigator is required to report Adverse Events/Device Deficiencies to the Sponsor within the following timeframes:

Type of event	Timeline for Reporting
SAE/SADE/UADE/ASADE/USADE	Immediately, but not later than 3 calendar days after investigation site study personnel's awareness of the event
All other AEs/ADEs	In a timely manner, usually within 7 calendar days after investigation site study personnel's awareness of the event
Device Deficiency	Immediately, but not later than 3 calendar days after investigation site study personnel's awareness of the event
Serious Health Threat	At the earliest possible opportunity, but not later than within 24 hours after investigation site study personnel's awareness of the event

Emergency contact for safety reporting:

CRO company:

Safety Department

E-mail: [contact]

Sponsor: Neptune Medical

E-mail: [contact]

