13. STATISTICAL DESIGN AND METHODS

13.1 Analysis Populations

The populations are defined as follows:

An enrolled patient is defined as all patients who met the inclusion/exclusion criteria and who provide written informed consent, meet the inclusion/exclusion criteria, and in whom the Vertex Catheter is introduced past the pulmonic valve.

The Intent-To-Treat (ITT) population is defined as all enrolled patients who met the inclusion/exclusion criteria and who provide written informed consent, and in whom the Vertex Catheter is introduced past the pulmonic valve; when Vertex Catheter is introduced past the pulmonic valve, and in whom the Vertex Pulmonary Embolectomy System is not able to access a pulmonary embolus.

All enrolled and ITT patients will be monitored per clinical investigation plan until the end of the required follow up period of 30 days.

This is a prospective, multicenter, single arm study designed to evaluate the safety and efficacy of the Vertex Pulmonary Embolectomy System for the aspiration of clot in patients with acute PE. The efficacy analysis will be conducted in the Intent-to-treat and per clinical investigation plan populations and the safety analysis will be conducted in all patients (enrolled, ITT, and procedural screen failures).

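### The plan contradicts itself on patients whose Vertex Catheter is inserted but does not cross the pulmonic valve, and their adverse events after study exit are not assured of capture

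*Combined protocol and SAP*

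**What the plan says.** **Enrolment.** The Abbreviations table fixes the moment: "enrollment occurs when Vertex Catheter is introduced past the pulmonic valve". Sections 2.6 and 13.1 use the same criterion. Section 13.1 promises monitoring to 30 days for enrolled and ITT patients only.

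**Patients who do not cross.** Section 2.8 counts among screen failures those who consented but "for whom the Vertex catheter was not introduced and past the pulmonic valve". Section 5.1.2 lists as an operative failure "Any eligible patient in whom the Vertex Catheter is not able to be introduced into the pulmonary artery for any reason" and then says "No further information will be collected on this patient; a study exit form (CRF) is required for all these patients". The exception that follows is for a patient with an adverse event after venous puncture but "in whom the Vertex Catheter is not inserted will be monitored through discharge for safety". The Terms and Definitions table is narrower: there an operative screen failure is an eligible patient in whom the catheter was not attempted or placed.

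**Patients never exposed.** Section 5.1.1 follows access failures to discharge if an adverse event occurs.

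**Rules pointing the other way.** Section 11.5 states: "Any adverse event/device deficiency occurring since subject signed ICF will be recorded", and continues recording until study exit. The procedural steps in Section 5 also call for adverse events, device deficiencies and technical complications to be recorded. Section 13.1 says "the safety analysis will be conducted in all patients (enrolled, ITT, and procedural screen failures", and Section 5.1, headed as procedural screen failure, contains both the access failures and the operative screen failures.

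**The concern.** A catheter that enters the sheath and stops short of the pulmonic valve may already have passed through the right heart. The plan foresees harm on that route. Section 10.1 names arrhythmia as the catheter advances through the right heart, and the glossary's examples of cardiac injury include "Tricuspid or Pulmonic valve damage". Section 5 has the procedure aborted for hemodynamic collapse or signs of vascular rupture. If that happens before the valve is crossed, the harm itself can turn the patient into a screen failure, so the classification is not independent of the safety outcome.

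Section 5.1 therefore gives a never-exposed patient an explicit safety provision and gives none to the exposed patient who did not cross. At stake is ascertainment of the primary safety endpoint (48 ± 8 hours, Section 6.1) and of the 30-day endpoints in Section 6.2: all-cause mortality, device-related serious adverse events and symptomatic recurrence. Section 2.6 continues enrolment until ten patients are enrolled and treated, so non-crossers come on top of the ten, and one event is a large share of the safety result.

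A secondary matter is the denominator. No set of patients in whom the catheter was inserted is defined, and the safety set in Section 13.1 mixes exposed and never-exposed patients.

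**Working it through.** The plan gives no event rate, performance goal or derivation for its ten patients, so there is no stated figure to reproduce. The check has two parts.

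**1. Which rule covers the patient whose catheter is inserted but does not cross?**

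- Sections 2.8 and 5.1.2: screen failure, with data collection stopped. The exception in 5.1.2 does not apply, because the catheter was inserted.
- Terms and Definitions: placement was attempted, so on a natural reading the patient is not an operative screen failure. Nor is the patient ITT. On this wording, membership of the Section 13.1 safety set is itself unclear.
- Sections 5 and 11.5: an event recognised before study exit is recorded.
- Section 5.1.2 requires an exit form but does not say when. The 48-hour visit (Section 9.3.1) and the 30-day visit (Section 9.3.2) are not assured, because Section 13.1 limits 30-day monitoring to enrolled and ITT patients.

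Events up to the exit form are therefore recordable under one rule and excluded under another. After the exit form, no rule assures ascertainment.

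**2. Size**

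Inputs: 10 enrolled (Section 2.6); *k* inserted but not crossed; *m* never exposed; *x*ₑ events in enrolled patients; *x*ₖ events in non-crossers. The documents give neither *k* nor *m*. The ranges used, *k* = 0–2 and *m* = 0–5, are assumptions.

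- A, exposed patients with all events captured: (*x*ₑ + *x*ₖ)/(10 + *k*)
- B, Sections 11.5 and 13.1 followed: (*x*ₑ + *x*ₖ)/(10 + *k* + *m*)
- C, Section 5.1.2 read literally within the Section 13.1 set: *x*ₑ/(10 + *k* + *m*)

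| *k* | *m* | *x*ₑ | *x*ₖ | A | B | C |
|---|---|---|---|---|---|---|
| 0 | 0 | 1 | 0 | 1/10 = 10.0% | 1/10 = 10.0% | 1/10 = 10.0% |
| 0 | 2 | 1 | 0 | 1/10 = 10.0% | 1/12 = 8.3% | 1/12 = 8.3% |
| 0 | 5 | 1 | 0 | 1/10 = 10.0% | 1/15 = 6.7% | 1/15 = 6.7% |
| 1 | 0 | 0 | 1 | 1/11 = 9.1% | 1/11 = 9.1% | 0/11 = 0% |
| 1 | 2 | 0 | 1 | 1/11 = 9.1% | 1/13 = 7.7% | 0/13 = 0% |
| 1 | 2 | 1 | 1 | 2/11 = 18.2% | 2/13 = 15.4% | 1/13 = 7.7% |
| 2 | 3 | 0 | 1 | 1/12 = 8.3% | 1/15 = 6.7% | 0/15 = 0% |

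Exact (Clopper–Pearson) 95% limits show how little precision there is: 1/11 gives 0.2% to 41.3% and 2/11 gives 2.3% to 51.8%. With no events, the upper limit is 1 − 0.025^(1/n): 30.8% at n = 10, 26.5% at n = 12 and 21.8% at n = 15. Adding never-exposed patients therefore tightens the apparent bound without adding information about the device. The plan does not itself call for intervals.

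A minus C is the effect of the conflict and the denominator together. A minus B is the denominator alone: 9.1 − 7.7 = 1.4 points in the fifth row. If *k* = 0 there is nothing to miss, and if *m* = 0 there is no dilution.

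**The case against.** The strongest reply is that the plan as a whole does not discard these events. Section 11.5 runs from consent and is not confined to enrolled patients. Its regulatory reporting of serious events with a causal or reasonably possible link to the device is not confined to them either. Section 5 requires recording at the procedure, and Section 13.1 brings procedural screen failures into the safety analysis. Section 7.6 restricts cardiac injury to damage during the index procedure, so an injury recognised on the table would be captured. The sentence stopping data collection also directly follows a bullet about patients converted before receiving any investigational treatment, and may have been written with them in mind.

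Most of this stands. A reader might infer that right-heart harm is simply lost and that the trial would report 0/10. The documents do not support that. Suppose twelve patients have the catheter inserted, two do not cross, and one of those two has an event. Sections 11.5 and 13.1 then give 1/12 = 8.3%. Even a literal Section 5.1.2 gives 0/12, because safety is not analysed in the enrolled patients alone.

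The reply does not cover injury recognised later, or bleeding, deterioration or death after the exit form. It also leaves a site that follows Section 5.1.2 to the letter in conflict with Section 11.5.

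On the denominator, it is fair to say that Section 13.2 is descriptive only, and that 1/13 and 1/10 describe the same single event.

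**Conclusion.** The point holds as an internal contradiction with a gap in follow-up. Terms and Definitions and Sections 2.8, 5.1.2, 11.5 and 13.1 cannot all be applied to a patient whose catheter is inserted but does not cross. For that patient, ascertainment after study exit is not assured for the remainder of the 48-hour MAE window or for the 30-day endpoints.

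The size depends on counts that the plan does not give. With one non-crosser who has the only event and two never-exposed patients, the reported rate could be 7.7% or 0%, against 9.1% among the exposed. With no such patients there is no effect. No test, margin or success rule changes, since the analysis is descriptive.

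Two further inferences should be resisted. Dilution is not established: it arises only if never-exposed patients occur and are counted. Nor does the point show that the effectiveness population is wrong. Navigation is one of several potential benefits in Section 1.4.2, no endpoint in Sections 6.3 and 6.4 measures it, and starting ITT at the pulmonic valve is partly a design preference.

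**What to change.** By amendment:

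1. Reconcile the operative-screen-failure entry in Terms and Definitions with Sections 2.8, 5.1.2, 11.5 and 13.1, so that a patient whose catheter is inserted but does not cross has one classification.
2. Remove the rule ending data collection for any patient in whom the Vertex Catheter was inserted.
3. Define the primary safety (MAE) set as all patients in whom the Vertex Catheter was inserted, with adverse-event ascertainment to 48 hours and 30 days, and make it the MAE denominator.
4. List adverse events of never-exposed procedural screen failures separately, outside that denominator.
5. Report failures to cross the pulmonic valve as x/N inserted.

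The enrolment and ITT point for effectiveness can stay where it is. The cost is amendment wording, follow-up of perhaps one or two extra patients (an assumption, as no rate is given), and an MAE figure that may look less favourable.

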5.1.3 Intent-To-Treat (ITT)

The Intent-To-Treat (ITT) population is defined as all enrolled patients who met the inclusion/exclusion criteria and who provide written informed consent, and in whom the Vertex Catheter is introduced past the pulmonic valve; when Vertex Catheter is introduced past the pulmonic valve, and in whom the Vertex Pulmonary Embolectomy System is not able to access a pulmonary embolus and will be monitored per clinical investigation plan until the end of the required follow up period of 30 days.

5.2 Adjunctive Treatment

Any use of thrombolytics during the procedure and up to 48-hours post-procedure will be considered a clinical investigation plan deviation and a treatment failure. The administration of thrombolytics to treat clinical deterioration will not be considered a clinical investigation plan deviation.

Adjunctive treatments will be considered as a clinical investigation plan deviation unless used to treat clinical deterioration. These adjunctive treatments will be recorded on the CRF.

Any use of adjunctive treatments for the purpose of reducing clot burden in the pulmonary artery (intra-procedure and up to 48 hours post procedure) will be considered a treatment failure.

6. STUDY OBJECTIVES

The Vertex Pulmonary Embolectomy System is a catheter-based mechanical thrombectomy device intended for use in the peripheral vasculature and for the treatment of pulmonary embolism. The Vertex Pulmonary Embolectomy System is designed to mechanically remove emboli and restore blood flow through the pulmonary arteries in patients experiencing acute PE.

The primary study objective is to evaluate the safety and effectiveness of the Vertex Pulmonary Embolectomy System for use in the removal of emboli in the treatment of acute intermediate risk pulmonary embolism.

6.1 Primary Endpoint - Safety

The study's primary safety endpoint is Major Adverse Events, which is a composite of:

- Device-related death within 48 hours (\pm 8 hours) of the procedure
- Major bleeding within 48 hours (\pm 8 hours) of the procedure
- Device-related adverse events within 48 hours (\pm 8 hours), including:
 - Clinical deterioration
 - Pulmonary vascular injury
 - Cardiac injury

